For Aim #2: Primary outcome variables: Presence of abnormalities in the four laryngeal functions and two swallowing physiology measures.

Statistical analysis: For each outcome and independent variable, a univariate logistic regression model will be developed.

Overall Sample Size Determination: In a simulated data analysis, a sample size of 200 yielded an area under the curve (AUC) of .75 for the resultant tree algorithm. To be conservative, we will enroll a total of 225 patients.

Significance: For the 455,000 acute respiratory failure (ARF) survivors each year, aspiration is a devastating complication that can develop after the initiation of oral nutrition.^{1,2} Occurring in as many as 44% of ARF survivors, aspiration is associated with many deleterious consequences including pneumonia, percutaneous feeding tube placement, long term care facility admission, and increased hospital

mortality.³⁻⁶ The complications of aspiration must be weighed against the consequences of inappropriately delaying the resumption of oral feeding. Delayed resumption of oral nutrition is associated with prolonged enteral tube feeding, increased caregiver burden, patient dissatisfaction, and increased health-related costs.⁷⁻¹⁰ Improving the ability to easily and accurately diagnose aspiration in ARF survivors would both reduce the frequency and severity of aspiration and limit the problems associated with delaying oral nutrition. *This proposal will develop an effective non-invasive bedside diagnostic clinical prediction rule (CPR) to detect aspiration in ARF survivors.*

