include the next branches on the trees. By splitting the data up into ten sets and choosing one set each time, ten-fold cross-validation will estimate the misclassification rate for the tree. The chosen set will be sent through a tree developed from randomly choosing nine of the sets. The misclassification for this set will be calculated, and performed 10 times until each set has been sent through a tree. An average rate of misclassification is developed to determine how well the tree based on all the data will perform on new data.

Sample Size Calculation and Feasibility: Based on our 18 month data from the two medical centers, there were a total of 1087 patients who remained on mechanical ventilation for at least 48 hours and lived to be discharged to home or self-care. For recursive partitioning, there are no specific sample size calculations. However, in a simulated data analysis, a sample size of 200 yielded an area under the curve (AUC) of .75 for the resultant tree algorithm. To be conservative, we will enroll a total of 225 patients. Based on our estimated number of ARF survivors, we will need to obtain consent from only 20.6% of them to achieve our enrollment goal. This is a very conservative estimate for obtaining informed consent for research on swallowing function.

Additional Considerations: Our primary analysis will develop a CPR for the combined outcome of silent and non-silent aspiration. We will also develop a CPR for silent aspiration alone defined as a PAS score =8, and a CPR for non-silent aspiration alone defined as a PAS score of 6-7. For each of the five different consistencies, the accuracy of the BSE assessment for aspiration will also be compared to the presence of aspiration of the FEES examination (PAS ≥6). Sensitivity, specificity, positive and negative predicted values will be determined with 95% confidence intervals for each point estimate. Based on a sample size of 225 patients, the width of each 95% confidence interval point estimate will be 2-4%.

Statistical analysis for Aim #2: For each outcome and independent variable, a univariate logistic regression model will be developed. If the Wald test for an individual variable in the logistic regression model is significant at the p <0.10 level, the variable will be included in a multivariable logistic regression model. ROC curves will be constructed to determine how well the regression models correctly predict

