whether the subject had the outcome of interest. Using baseline demographical information, testing for confounding will also be assessed to better understand the relationships between independent variables and outcomes. Based on the enrollment described in Aim #1, we have powered the univariate comparison between our primary independent and dependent variables for these studies. A logistic regression with a sample size between 178 and 271 observations achieves 80% power at a 0.05 significance level to detect an odds ratio between 2.5 and 3.0.

Risks and Justifications of Procedures and Data Collection Tools: Risks of the FEES procedure include patient discomfort, gagging, vomiting, aspiration, mucosal injury, epistaxis, and an adverse reactions to topical anesthetics.^{12, 15-17} One study of 500 consecutive FEES assessments reported the occurrence of minor epistaxis with spontaneous cessation of bleeding in 0.6% of cases.¹⁵ Another survey of SLPs performing a total of 6000 FEES examinations reported 20 cases of epistaxis (0.3%).¹⁸ Vasovagal syncope and laryngospasm, while theoretical concerns, have been shown to occur exceedingly infrequently (a total of two and four cases, respectively, ever reported out of all FEES procedures ever done).¹⁸ None of these reported cases resulted in serious consequences.¹⁸ The 3-WST has been shown to be a safe test in large groups of hospitalized patients.^{11, 19} Our informed consent process will involve a complete discussion of each of these risks, citing reported frequencies of adverse events. Due to the risk of breach of confidentiality, we have assured that all data will be collected and stored in a safe manner. All data at each site, will be stored on a password protected research-specific server, and will not be transferred to any other computer or flash drive. Hard copies of consent forms and other forms will be kept in a locked drawer in a locked office at each enrolling site. Citrix ShareFile, a cloud-based, encrypted HIPAA compliant and University of Colorado IT approved application will be used to share de-identified FEES video recordings between the two enrolling sites. ShareFile will be accessible only to approved research staff and used for the fidelity and scoring of FEES procedures by investigators.

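### Aim 2 names no internal validation for its ROC curves, so the AUC of models screened and fitted on the same patients will be optimistic

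*Combined protocol and SAP*

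**What the plan says.** The section on statistical analysis for Aim #2 gives three steps in order.

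1. "For each outcome and independent variable, a univariate logistic regression model will be developed".
2. If a variable's Wald test is "significant at the p <0.10 level", "the variable will be included in a multivariable logistic regression model".
3. "ROC curves will be constructed to determine how well the regression models correctly predict" "whether the subject had the outcome of interest".

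Nothing in that section says on which patients the curves are drawn, and no resampling, held-out sample or shrinkage is named. The only other patients linked to Aim 2 are the 59 from the second centre, described under Preliminary Data, and they are not assigned to validation. In the Aim #1 analysis section, by contrast, "ten-fold cross-validation will estimate the misclassification rate for the tree", with the stated purpose of judging performance on new data.

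The sample size section says "we will enroll a total of 225 patients". The opening summary gives the Aim 2 primary outcome variables as "Presence of abnormalities in the four laryngeal functions and two swallowing physiology measures", which is six items. The number of candidate predictors per model and the expected rates of the Aim 2 outcomes are not given.

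**The concern.** An AUC computed on the patients who chose the variables and supplied the coefficients is an apparent AUC. Two things raise it above the value that new patients would show. The screen keeps the variables that separated the groups best in this sample, including by chance, and the fit then points each coefficient in the direction that this sample favours. The plan gives the ROC curve the job of saying how well the models predict, and an apparent AUC does that job with a known upward bias.

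At stake is the predictive ability reported for the Aim 2 models. A set of abnormalities with no real information, if it yields a model at all, would be reported with an AUC above 0.5. A set with modest information would look somewhat better than it is. The protocol guards against this for the Aim 1 tree and does not for Aim 2.

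**Working it through.** **The plan's own figures.** The plan states no AUC for Aim 2, so there is none to reproduce. Its one Aim 2 figure is that 178 to 271 observations give 80% power at 0.05 for odds ratios of 2.5 to 3.0. The standard (Hsieh) formula for a binary covariate, two-sided, gives 271 for OR 2.5 and 180 for OR 3.0 if the baseline risk is 0.16 and the exposure prevalence 0.25. Neither input is stated, so the range can be neither confirmed nor refuted. It is used here only as the source of the plan's effect sizes.

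**Inputs from the protocol.** N = 225; screen at p<0.10; aspiration rate 44% (upper literature figure in the Background) or 50% (pilot, 26 patients); OR 2.5-3.0.

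**Assumed inputs.** Candidates per model: 6 (the named abnormalities) up to 15 (13 structural rows on the FEES form plus two physiology measures), with 1 to 30 as a wider range. Candidates are independent; binary ones have 30% prevalence unless stated.

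**Does a model get fitted when nothing is associated?** With k independent candidates, P(at least one passes) = 1 - 0.9^k.
- k = 6: 1 - 0.531 = 0.469, so no variable enters in about 53% of data sets.
- k = 14: 0.771. k = 15: 0.794.

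**One null variable, by hand.** For a single binary variable, apparent AUC = 0.5 + |p1 - p0|/2, where p1 and p0 are its frequencies in patients with and without the outcome. At 44% the groups are 99 and 126. At 30% prevalence the standard error of p1 - p0 is sqrt(0.3 × 0.7 × (1/99 + 1/126)) = 0.0615.
- To pass the screen, |p1 - p0| must exceed about 1.645 × 0.0615 = 0.101, so the AUC is at least about 0.5 + 0.101/2 = 0.55.
- Given that it passes, the mean |z| is 2 × 0.1031/0.10 = 2.06, so the mean AUC is about 0.5 + 2.06 × 0.0615/2 = 0.56. The true value is 0.50.

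**Several candidates, by simulation of the written procedure** (screen, fit, ROC on the same patients; N = 225, no association). The AUC is the mean among data sets in which a model was fitted.

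| Setting | Mean apparent AUC |
|---|---|
| 6 candidates, 44% outcome: binary / mixed / continuous | 0.576 / 0.582 / 0.587 |
| 6 candidates, 50% outcome: binary / continuous | 0.574 / 0.586 |
| 6 binary candidates at 10% prevalence, 44% outcome | 0.55 |
| 14 candidates, 44% outcome | 0.59-0.60 |
| 30 candidates, 44% outcome | 0.63-0.64 |
| 6 candidates, 20% outcome | 0.59-0.61 |
| 6 candidates, 10% outcome | 0.62-0.65 |

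On new patients the fitted null models average 0.50. Every fitted null model had an apparent AUC above 0.5 (lowest 0.525). With 6 candidates and a 44% outcome the 95% interval excluded 0.5 in about 61-64% of fitted models. Counting data sets with no model as 0.50, the 6-candidate mean is 0.53-0.54; for binary candidates, 0.531 × 0.50 + 0.469 × 0.576 = 0.536.

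**With one real predictor at the plan's odds ratios** (binary candidates, 44% outcome):

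| OR | Candidates | Apparent | New patients | Optimism |
|---|---|---|---|---|
| 2.5 | 6 | 0.617 | 0.590 | 0.026 |
| 3.0 | 6 | 0.634 | 0.612 | 0.022 |
| 2.5 | 14 | 0.636 | 0.582 | 0.054 |
| 3.0 | 14 | 0.653 | 0.607 | 0.046 |

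A separate run with 15 candidates at OR 2.5 gave 0.64 against 0.58.

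**Does the correction work?** With the screen and fit repeated in each bootstrap resample, and a true OR of 2.0, the corrected AUC was 0.566 against a true 0.564 (6 candidates) and 0.555 against 0.555 (15). Among null models that were fitted, it fell from 0.580 to 0.536 (6) and from 0.599 to 0.523 (14).

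**The case against.** Aim 2 is mainly about association. Its objective is to find abnormalities linked to aspiration, its power statement concerns univariate comparisons, and the ROC curve is a supporting description with no threshold, test or success rule attached. That stands, and it limits the consequence: the bias does not change which abnormalities are reported as associated. The plan nevertheless gives the curve a predictive purpose, and the number reported for it should be sound.

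The summary lists the six abnormalities as outcomes, whereas the main calculations treat them as predictors of aspiration. That also stands as a limit on the exact figures. The direction is the same on either reading, and the null AUC is higher if the modelled outcome is less common than aspiration (see the 20% and 10% rows). Fifteen candidates is a generous count, because it treats left and right rows of the FEES form as separate.

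A reader might infer that a useless set of abnormalities would always appear to predict, or that an AUC of 0.57-0.59 under no association is a property of the plan. The documents do not support either. With six independent candidates, about half of null data sets produce no model at all. Among those that do, the interval still includes 0.5 in over a third at a 44% outcome rate. The 0.57-0.59 range depends on a candidate count and an outcome rate that the plan does not state.

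That the same patients are used throughout is inferred from silence, but no other data set is offered.

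**Conclusion.** The concern holds as a bias of modest size in a supporting measure. As written, the Aim 2 AUC will be optimistic, and the plan has no step that would reveal by how much. Under no association, and given that a model is fitted, the mean apparent AUC is about 0.57-0.60 (6 to 15 candidates, 44-50% outcome) and about 0.55-0.65 over wider assumptions, against 0.50. At the plan's odds ratios the excess is about 0.02-0.03 with 6 candidates and 0.05-0.06 with 14-15. These sizes rest on assumed candidate counts, prevalences and independence; the direction does not. The odds ratios and the list of associated abnormalities are outside this point.

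**What to change.** Extend the ROC sentence in the Aim #2 analysis section along these lines:

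*The AUC of each Aim 2 model will be corrected for optimism by bootstrap (or cross-validation), repeating the univariate screen and the multivariable fit in every resample. A resample in which no variable passes the screen will be scored as an intercept-only model with AUC 0.5. The corrected AUC with its interval will be the reported result, shown beside the apparent AUC.*

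Listing the candidate variables for each model in the same place would let a reader judge the likely optimism.

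The cost is a few lines of code, with no new patients or data. There are two downsides. The reported AUC will be less favourable. The correction also removes only part of the bias among null models that happened to be selected, leaving a mean of about 0.52-0.54, so a corrected AUC in that region should not be read as evidence of prediction.

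### Aim 2's power sentence covers 178 to 271 observations rather than the planned 225: the case needing 271 has about 72% power at 225, and no odds ratio detectable at 225 is given

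*Combined protocol and SAP*

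**What the plan says.** Enrolment is a single number. *Overall Sample Size Determination* in the opening summary and *Sample Size Calculation and Feasibility* under Aim 1 both say "To be conservative, we will enroll a total of 225 patients". That number comes from a simulation for the Aim 1 tree, not from an Aim 2 calculation.

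For Aim 2 the analysis is: "For each outcome and independent variable, a univariate logistic regression model will be developed". *Statistical analysis for Aim #2* then ties the power to the Aim 1 number: "Based on the enrollment described in Aim #1, we have powered the univariate comparison between our primary independent and dependent variables". The support offered is one sentence: "A logistic regression with a sample size between 178 and 271 observations achieves 80% power at a 0.05 significance level", for the purpose "to detect an odds ratio between 2.5 and 3.0".

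The sentence does not give:
- power, or a detectable odds ratio, at 225;
- which sample size belongs to which odds ratio;
- the outcome rate or the predictor distribution;
- whether the 0.05 level is one-sided or two-sided.

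The same section carries a variable into the multivariable model if its univariate Wald test reaches p<0.10.

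**The concern.** A power statement should tell the reader what effect the planned number of patients can detect. Here the plan points to 225 and then quotes a range whose upper end is 271 - 225 = 46 patients above enrolment (46/225 = 20.4%). Whatever case needed 271 observations for 80% power cannot have 80% power with 225.

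At stake is how Aim 2, one of the study's two aims, is interpreted. A reader who takes 80% as applying throughout would put the chance of missing a true effect at 20%, when for one end of the range it is nearer 28% at the 0.05 level.

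**Working it through.** **Inputs from the plan.** n = 225 (*Sample Size Calculation and Feasibility*). N = 178 and 271, power 80%, level 0.05, odds ratios 2.5 and 3.0 (*Statistical analysis for Aim #2*). Sidedness is not stated, so both are run.

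**1. Can 178 and 271 be reproduced?** Not uniquely, because the outcome rate and predictor prevalence are missing. They can be attained. Take the Hsieh formula for a binary predictor:

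N = {z_α √[P(1−P)/B] + z_β √[P1(1−P1) + P2(1−P2)(1−B)/B]}² / [(P1−P2)²(1−B)]

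Here B is the predictor prevalence, P1 and P2 are the outcome risks without and with the predictor, and P is the overall risk. Assume P1 = 12% and B = 38%, two-sided 0.05. (These inputs are mine, not the plan's.)
- Odds ratio 2.5: P2 = 0.254, N = 271.
- Odds ratio 3.0: P2 = 0.290, N = 179.

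Other assumed inputs give similar pairs. The range is therefore not shown to be wrong.

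**2. Power at 225.** If a case needs N for 80% power, and the standard error scales with 1/√n, then

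power = Φ[(z_α + 0.842) √(225/N) − z_α].

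- N = 271, two-sided: Φ(2.802 × 0.911 − 1.960) = Φ(0.593) = 72.3%; miss probability 27.7%.
- N = 178, two-sided: Φ(2.802 × 1.124 − 1.960) = Φ(1.190) = 88.3%.
- One-sided 0.05 (1.645 for 1.960): 73.3% and 87.5%.

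No prevalence enters this formula. As a check, the full Hsieh formula (two-sided) was run over assumed baseline risks of 5–60% and predictor prevalences of 5–95%. Every combination needing about 271 gave 70.7–73.5% at 225.

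**3. Odds ratio detectable with 80% power at 225.** Scaling the log odds ratio: OR = exp[ln(OR₀) √(N/225)].

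| Pairing (not stated in the plan) | From N = 271 | From N = 178 |
|---|---|---|
| 271 with 2.5, 178 with 3.0 | exp(0.916 × 1.097) = 2.73 | exp(1.099 × 0.889) = 2.66 |
| 271 with 3.0, 178 with 2.5 | exp(1.099 × 1.097) = 3.34 | exp(0.916 × 0.889) = 2.26 |

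Interpolating ln(OR) on 1/√N under the first pairing gives 2.70. That pairing is consistent with a single set of inputs: N × (ln OR)² is 271 × 0.840 = 228 and 178 × 1.207 = 215, within about 6%. The second would require the two sample sizes to come from different variables. Aim 2 has six measures (four laryngeal, two swallowing), so this cannot be excluded.

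**4. The p<0.10 screen.** If 271 is a two-sided 0.05 figure, power at 225 for a two-sided 0.10 test is Φ(2.802 × 0.911 − 1.645) = Φ(0.908), about 82%. If 271 was computed one-sided at 0.05, the critical value is already 1.645 and the 73.3% stands.

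**The case against.** The strongest reply is that the sentence is a bracket. The midpoint of 178 and 271 is (178 + 271)/2 = 224.5, almost exactly the planned number. On that reading the plan says openly that the smaller effects need more than 225 and the larger ones fewer, and with the smaller odds ratio needing the larger sample the detectable value of about 2.7 falls inside 2.5–3.0. This largely stands: on that reading the sentence is coarse rather than false. It does not supply the missing figure, though, and it depends on a pairing the plan leaves out.

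A second reply is that little depends on it. Variables enter the multivariable model at p<0.10, where the 271 case has about 82% power if 271 is two-sided. No decision rule rests on a null univariate result, and Aim 1 set the enrolment. This also stands and limits the consequence.

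A reader might infer more than the documents support:
- *That 178–271 is an arithmetic error.* The inputs needed to test it are missing, and plausible ones reproduce it.
- *That the study needs 271 patients.* The plan does not commit to 80% power at every odds ratio in its range, and does not clearly promise 2.5 at 225.
- *That real associations would be lost at a 28% rate.* That figure belongs to the 0.05 level and the 271 case only; the plan's selection step uses 0.10.

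**Conclusion.** The point holds as an incomplete power statement with a shortfall at one end, not as a wrong calculation. With 225 patients, 80% power at 0.05 does not extend across the stated range: it is about 72% for the case needing 271 (73% one-sided) and about 88% for the case needing 178. If 271 belongs to an odds ratio of 2.5, the claim fails at that end and becomes true from about 2.7. If 271 belongs to 3.0, that case reaches 80% power only at about 3.34, beyond the stated range.

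The power figures rest on the plan's own numbers, on standard errors scaling with 1/√n, and on all 225 patients giving analysable data; missing examinations would lower them. The detectable odds ratios rest in addition on the unstated pairing. Given the p<0.10 screen and the absence of any decision tied to a null result, the importance lies between minor and should-fix.

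**What to change.** Replace the range in *Statistical analysis for Aim #2* with a statement at the planned number, for example: With 225 patients and a [one-/two-]sided 0.05 level, the univariate logistic regression of [outcome] on [predictor] has 80% power to detect an odds ratio of [value], assuming an outcome rate of [x] and a predictor prevalence of [y].

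Take the values from the power calculation rerun at n=225. Do not insert 2.7 by default; it applies only if 271 went with 2.5 and 178 with 3.0. If the two sample sizes came from different variables, give one value for each.

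The outcome and predictor must be named first. The opening summary lists the laryngeal and swallowing abnormalities as the Aim 2 outcomes, while the aim concerns their association with aspiration, and the outcome rate means nothing until the roles are fixed.

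The cost is one rerun and a short rewrite, or a few lines if values differ by variable. It adds no patients and changes no endpoint or analysis. The only downside is a slightly less favourable stated effect.
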